An adverse event or suspected adverse reaction is considered “life-threatening” if, in the view of either the investigator or sponsor, its occurrence places the patient or subject at immediate risk of death. It does not include an adverse event or suspected adverse reaction that, had it occurred in a more severe form, might have caused death.

Drug Profile and Side Effects

Trade Drug Name: Not applicable

Generic Drug Name: Amitriptyline

Investigational Drug Name:

Identify the name of the manufacturer or source of investigational drug/biologic:

Is the drug supplied at no cost? Yes

Is the Drug FDA Approved: Yes

Is this a new drug or a new use of an already approved drug Yes

Is an IND necessary No

IND Number

Who holds the IND: N/A

IND details:

The drug being used will be amitriptyline capsules compounded by the Investigational Drug Service at BMC. We believe our use meets the requirements for an IND exemption as per 21 CFR 312.2.

If FDA Approved and an IND is not required, Please provide a rationale for exemption:

As previously mentioned in part D, we believe that the risks of amitriptyline are well-characterized, and not out of proportion to the benefits for patients. Furthermore, this is one of the standard medications used at BMC by otolaryngologists to treat chronic laryngitis felt to be possibly resulting from neuropathy, and has been used successfully for hundreds of patients for this purpose. In a recent analysis of over 50 patients given amitriptyline for this purpose at BMC, over half had significant improvement, and less than 10% had to discontinue use because of side-effects.

In addition, this study is not intended to change the indication or marketing for amitriptyline in any way. Nor will the study involve any marketing or commercial activity.

Lastly, the study will follow the guidelines set forth in part 50 and 56, as outlined in the applicable sections of this proposal.

Are you currently using this IND in another research project? No

If yes, list the IRB Number(s):

Dose Range: 0-50 mg

Frequency: qhs

Route of administration: PO

Will the investigational pharmacy be dispensing? Yes

If the source is not a FDA licensed facility, provide details regarding the purity, quality,

stability and sterility of the investigational drug/biologic:

Identify who will be preparing the investigational drug/biologic for administration and describe in detail how it will be prepared:

Amitriptyline 12.5mg and matching placebo capsules will be compounded by IPS at BMC using Avicel as the placebo and inert filler.

Indication(s) under Investigation:

Chronic laryngitis

Where will the drug be stored

IPS at BMC.

Drug Storage Restrictions (including temperature, etc.):

Controlled Room Temperature (15°-30°C)

Administration Instructions:

The medication will be given in 12.5mg capsules. Patients will take one capsule before bed for one week. The patient may increase dosage by one 12.5mg tablet each week if no improvement and no adverse side effects are noted, up to four 12.5mg capsules every night at bedtime for a maximum dose of 50mg daily. If any adverse side effects are noted, the patient may decrease the dosage to the last well-tolerated dose. Patients are counseled not to completely discontinue treatment without consulting the PI first.

The most common side effects of amitriptyline are:

- 1) Feeling lightheaded, sleepy, having blurred vision, or a change in thinking clearly.
- 2) Feeling dizzy
- 3) Constipation
- 4) Dry mouth
- 5) Change in color of urine to blue or green.

All potential side effects include:

Cardiovascular: Orthostatic hypotension, tachycardia, ECG changes (nonspecific), AV conduction changes, cardiomyopathy (rare), MI, stroke, heart block, arrhythmia, syncope, hypertension, palpitation

Central nervous system: Restlessness, dizziness, insomnia, sedation, fatigue, anxiety, cognitive function impaired, seizure, extrapyramidal symptoms, coma, hallucinations, confusion, disorientation, coordination impaired, ataxia, headache, nightmares, hyperpyrexia

Possible Untoward Effects, Their Symptoms & Treatment:

Dermatologic: Allergic rash, urticaria, photosensitivity, alopecia

Endocrine & metabolic: Syndrome of inappropriate ADH secretion

Gastrointestinal: Weight gain, xerostomia, constipation, paralytic ileus, nausea, vomiting, anorexia, stomatitis, peculiar taste, diarrhea, black tongue

Genitourinary: Urinary retention Hematologic: Bone marrow depression, purpura, eosinophilia

Neuromuscular & skeletal: Numbness, paresthesia, peripheral neuropathy, tremor, weakness

Ocular: Blurred vision, mydriasis, ocular pressure increased

Otic: Tinnitus

Potential or Actual Antidotes for Excessive or Adverse Drug Effect:

Sodium bicarbonate can be used in cases of overdose with cardiac effects.

Contraindications: Hypersensitivity to amitriptyline or any component of the formulation (cross-sensitivity with other tricyclics may occur); use of MAO inhibitors within past 14 days; acute recovery phase following myocardial infarction; concurrent use of cisapride

Interactions:

Acetylcholinesterase Inhibitors (Central): Anticholinergics may diminish the therapeutic effect of Acetylcholinesterase Inhibitors (Central). Acetylcholinesterase Inhibitors (Central) may diminish the therapeutic effect of Anticholinergics. If the anticholinergic action is a side effect of the agent, the result may be beneficial.

Risk

C: Monitor therapy

Alcohol (Ethyl): CNS Depressants may enhance the CNS depressant effect of Alcohol (Ethyl). Risk C: Monitor therapy

Alfuzosin: May enhance the QTc-prolonging effect of QTc-Prolonging Agents. Risk C: Monitor therapy

Alpha-/Beta-Agonists (Direct-Acting): Tricyclic Antidepressants may enhance the vasopressor effect of Alpha-/Beta-Agonists (Direct-Acting). Exceptions: Dipivefrin. Risk D: Consider therapy modification

Alpha1-Agonists: Tricyclic Antidepressants may enhance the vasopressor effect of Alpha1-Agonists. Risk D: Consider therapy modification

Contraindications and Interactions, If Known:

Alpha2-Agonists: Tricyclic Antidepressants may diminish the antihypertensive effect of Alpha2-Agonists. Exceptions: Apraclonidine; Brimonidine. Risk D: Consider therapy modification

Altretamine: May enhance the orthostatic hypotensive effect of Tricyclic Antidepressants. Risk C: Monitor therapy

Amphetamines: Tricyclic Antidepressants may enhance the stimulatory effect of Amphetamines. Tricyclic Antidepressants may also potentiate the cardiovascular effects of Amphetamines. Risk C: Monitor therapy

Anticholinergics: May enhance the adverse/toxic effect of other Anticholinergics. Exceptions: Levocabastine (Nasal); Levocabastine (Ophthalmic); Paliperidone. Risk C: Monitor therapy

Artemether: May enhance the QTc-prolonging effect of QTc-Prolonging Agents. Risk X: Avoid combination

Aspirin: Antidepressants (Tricyclic, Tertiary Amine) may enhance the antiplatelet effect of Aspirin. Risk C: Monitor therapy

Barbiturates: May increase the metabolism of Tricyclic Antidepressants. Risk D: Consider therapy modification

Beta2-Agonists: Tricyclic Antidepressants may enhance the

adverse/toxic effect of Beta2-Agonists. Risk C: Monitor therapy
BuPROPion: May decrease the metabolism of Tricyclic Antidepressants. Risk C: Monitor therapy

CarBAMazepine: May increase the metabolism of Tricyclic Antidepressants. Risk C: Monitor therapy

Chloroquine: May enhance the QTc-prolonging effect of QTc-Prolonging Agents. Risk C: Monitor therapy

Cimetidine: May decrease the metabolism of Tricyclic Antidepressants. Risk C: Monitor therapy

Cinacalcet: May increase the serum concentration of Tricyclic Antidepressants. Risk C: Monitor therapy

Ciprofloxacin: May enhance the QTc-prolonging effect of QTc-Prolonging Agents. Risk C: Monitor therapy

Ciprofloxacin (Systemic): May enhance the QTc-prolonging effect of QTc-Prolonging Agents. Risk C: Monitor therapy

Cisapride: Amitriptyline may enhance the arrhythmogenic effect of Cisapride. Risk X: Avoid combination

CNS Depressants: May enhance the adverse/toxic effect of other CNS Depressants. Exceptions: Epinastine; Levocabastine (Nasal); Levocabastine (Ophthalmic); Olopatadine; Olopatadine (Ophthalmic). Risk C: Monitor therapy

Conivaptan: May increase the serum concentration of CYP3A4 Substrates. Management: Upon completion/discontinuation of conivaptan, allow at least 7 days before initiating therapy with drugs that are CYP3A4 substrates. Risk D: Consider therapy modification

CYP2D6 Inhibitors (Moderate): May decrease the metabolism of CYP2D6 Substrates. Risk C: Monitor therapy

CYP2D6 Inhibitors (Strong): May decrease the metabolism of CYP2D6 Substrates. Risk D: Consider therapy modification

Desmopressin: Tricyclic Antidepressants may enhance the adverse/toxic effect of Desmopressin. Risk C: Monitor therapy

Dexmethylphenidate: May enhance the adverse/toxic effect of Tricyclic Antidepressants. Dexmethylphenidate may increase the serum concentration of Tricyclic Antidepressants. Risk C: Monitor therapy

Divalproex: May increase the serum concentration of Tricyclic Antidepressants. Risk C: Monitor therapy

Dronedarone: QTc-Prolonging Agents may enhance the QTc-prolonging effect of Dronedarone. Risk X: Avoid combination

DULoxetine: May decrease the metabolism of Tricyclic Antidepressants. Risk C: Monitor therapy

Gadobutrol: May enhance the QTc-prolonging effect of QTc-Prolonging Agents. Risk D: Consider therapy modification

Iobenguane I 123: Tricyclic Antidepressants may diminish the therapeutic effect of Iobenguane I 123. Risk X: Avoid combination
Lithium: May enhance the neurotoxic effect of Tricyclic Antidepressants. Risk C: Monitor therapy

Lumefantrine: May enhance the QTc-prolonging effect of QTc-Prolonging Agents. Risk X: Avoid combination

MAO Inhibitors: May enhance the serotonergic effect of Tricyclic Antidepressants. This may cause serotonin syndrome. Risk X: Avoid combination

MAO Inhibitors: May enhance the orthostatic hypotensive effect of Orthostatic Hypotension Producing Agents. Risk C: Monitor therapy

Methylphenidate: May enhance the adverse/toxic effect of Tricyclic Antidepressants. Methylphenidate may increase the serum concentration of Tricyclic Antidepressants. Risk C: Monitor therapy

Metoclopramide: May enhance the adverse/toxic effect of Tricyclic Antidepressants. Management: Seek alternatives to this combination when possible. Monitor patients receiving metoclopramide with tricyclic antidepressants for signs of extrapyramidal symptoms, neuroleptic malignant syndrome, and serotonin syndrome. Risk D: Consider therapy modification

Nilotinib: May enhance the QTc-prolonging effect of QTc-Prolonging Agents. Risk X: Avoid combination

NSAID (COX-2 Inhibitor): Antidepressants (Tricyclic, Tertiary Amine) may enhance the antiplatelet effect of NSAID (COX-2 Inhibitor). Risk C: Monitor therapy

NSAID (Nonselective): Antidepressants (Tricyclic, Tertiary Amine) may enhance the antiplatelet effect of NSAID (Nonselective). Risk C: Monitor therapy

Peginterferon Alfa-2b: May decrease the serum concentration of CYP2D6 Substrates. Risk C: Monitor therapy

Pimozide: QTc-Prolonging Agents may enhance the QTc-prolonging effect of Pimozide. Risk X: Avoid combination

Pramlintide: May enhance the anticholinergic effect of Anticholinergics. These effects are specific to the GI tract. Risk D: Consider therapy modification

Propoxyphene: May enhance the CNS depressant effect of Tricyclic Antidepressants. Risk C: Monitor therapy

Protease Inhibitors: May increase the serum concentration of Tricyclic Antidepressants. Risk C: Monitor therapy

QTc-Prolonging Agents: May enhance the adverse/toxic effect of other QTc-Prolonging Agents. Their effects can be additive, causing life-threatening ventricular arrhythmias. Risk D: Consider therapy modification

QuiNIDine: Tricyclic Antidepressants may enhance the QTc-prolonging effect of QuiNIDine. QuiNIDine may increase the

serum concentration of Tricyclic Antidepressants. Risk D: Consider therapy modification

QuiNINE: QTc-Prolonging Agents may enhance the QTc-prolonging effect of QuiNINE. QuiNINE may enhance the QTc-prolonging effect of QTc-Prolonging Agents. Risk X: Avoid combination

Selective Serotonin Reuptake Inhibitors: May decrease the metabolism of Tricyclic Antidepressants. Risk D: Consider therapy modification

Serotonin Modulators: May enhance the adverse/toxic effect of other Serotonin Modulators. The development of serotonin syndrome may occur. Risk D: Consider therapy modification

Sibutramine: May enhance the serotonergic effect of Serotonin Modulators. This may cause serotonin syndrome. Risk X: Avoid combination

St Johns Wort: May increase the metabolism of Tricyclic Antidepressants. The risk of serotonin syndrome may theoretically be increased. Risk D: Consider therapy modification

Sulfonylureas: Cyclic Antidepressants may enhance the hypoglycemic effect of Sulfonylureas. Risk C: Monitor therapy

Terbinafine: May decrease the metabolism of Tricyclic Antidepressants. Risk D: Consider therapy modification

Terbinafine (Systemic): May decrease the metabolism of Tricyclic Antidepressants. Risk D: Consider therapy modification

Tetrabenazine: QTc-Prolonging Agents may enhance the QTc-prolonging effect of Tetrabenazine. Risk X: Avoid combination

Thioridazine: QTc-Prolonging Agents may enhance the QTc-prolonging effect of Thioridazine. Risk X: Avoid combination

TraMADol: Tricyclic Antidepressants may enhance the neuroexcitatory and/or seizure-potentiating effect of TraMADol. Risk C: Monitor therapy

Valproic Acid: May increase the serum concentration of Tricyclic Antidepressants. Risk C: Monitor therapy

Vitamin K Antagonists (eg, warfarin): Tricyclic Antidepressants may enhance the anticoagulant effect of Vitamin K Antagonists. Risk C: Monitor therapy

Yohimbine: Tricyclic Antidepressants may increase the serum concentration of Yohimbine. Risk C: Monitor therapy

Ziprasidone: QTc-Prolonging Agents may enhance the QTc-prolonging effect of Ziprasidone. The risk of a severe arrhythmia may be increased. Risk X: Avoid combination

Investigators Authorized to Prescribe:

[name]

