The target of our study is to have 100 subjects complete the study, excluding prior pilot study data. We will run a blinded interim analysis on the primary endpoint when 25 subjects in each arm have completed treatment and follow-up, and a conditional power for detecting a significant treatment effect by the planned end of the study (100 subjects) will be determined. If this conditional power is between 50 and 80%, the sample size will be recalculated to achieve 80% conditional power following the algorithm of Chen and DeMets (2004). Otherwise, the study will continue until 100 patients have completed treatment.

Based on prior pilot study data, we anticipate the study dropout rate to be approximately 30%, from time of initial enrollment to completion of the post-treatment survey. During the prior pilot study, the dropout rate was 50% initially, and dropped to 30% during the last 8 months of enrollment, until the study was closed. Dropout rate was the same in each arm, with 5 subjects in each arm dropping out after starting treatment. Only three subjects cited adverse events (AEs) as a reason for drop out; two subjects on placebo complained of headache and dry mouth, respectively, and one subject on amitriptyline complained of sedation.

Thus, we anticipate a dropout rate during treatment of 30%, and anticipate having to enroll at least 75 subjects in order for 25 patients in each arm to complete the study by the interim analysis.

The physician may elect to discontinue study drug due to serious adverse events (SAEs) or unintended pregnancy. If a subject withdraws from treatment due to adverse events, we will ask that they continue coming in for follow-up visits and finish the remaining parts of the visits off the study drug.

The primary endpoint of the trial will be the total modified RSI at 8 weeks. The Reflux Symptom Index (RSI) has been validated by Belfasky et. al. [Belafsky PC, Postma GN, Koufman JA. Validity and reliability of the reflux symptom index (RSI). *Journal of Voice*. 2002;16:274-277]. The RSI is a questionnaire consisting of 9 statements to be ranked 0-5. We have added two additional symptoms to be assessed with the RSI, "throat pain or burning" and "pain with swallowing", which we believe are also relevant to chronic laryngeal neuropathy.

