When 25 subjects in each arm (placebo and amitriptyline) have completed the study and follow-up (i.e. at least 50 subjects total), a blinded interim analysis will be performed, and conditional power for detecting a significant treatment effect by the planned end of the study (100 subjects) will be determined. If this conditional power is between 50 and 80%, the sample size will be recalculated to achieve 80% conditional power following the algorithm of Chen and DeMets (2004). Otherwise, the study will continue until 50 subjects in each arm have completed treatment.

For data analysis, we will be performing both per-protocol and multiple imputation approach analyses. Multiple imputation using the linear regression approach will be used to impute missing data, for subjects who do not complete treatment. Intention-to-treat analysis is not possible, since our outcomes are determined by the 8 week post-treatment survey, and there are no intermediate data points with regards to treatment efficacy outcomes (ie, subjects who drop out will not have any outcomes recorded).

The primary outcome measure will be the pre- and post- treatment difference in scores on the Reflux Symptom Index (RSI), with two additional questions added to assess for symptoms that may be more specific to chronic laryngeal neuropathy.

The RSI is a validated questionnaire consisting of 9 statements to be ranked 0-5. We have added two additional symptoms to be assessed to the RSI, "throat pain or burning" and "pain with swallowing", which we believe may also be relevant to chronic laryngeal neuropathy.

The modified RSI score will be averaged for each group (amitriptyline vs. placebo), and since it is a nearly continuous variable (with an expected normal distribution) and we will

be comparing the mean of the change rather than categorizing the treatment into responder and non-responders, we will also analyze it using an Analysis of Covariance or Wilcoxon Rank Sum test if determined to have a non-normal distribution.

For the modified RSI, we will also conduct a secondary analysis looking at change in severity of each symptom individually. This will account for questions that may be less relevant to laryngitis overall (and more specific to reflux).

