The treatment assignment will not be available to the clinical staff that will administer the study questionnaires and analyze resulting data while subjects are receiving the study drug or placebo, except in case of severe adverse side effect or other emergency requiring urgent unblinding. If emergency unblinding is required as noted by the PI or study staff, they will contact the IPS on-call personnel who will have access to the randomization table.

On Days 7, 14, 21, 28, 35, 42, 49, and 56 of the study the subject will be contacted by phone by a blinded study coordinator. The subject will be asked about side-effects and concerns, and confirm the dose they are taking that week. The study coordinator will relay any medical concerns to the primary investigator for consideration and follow-up, or to the nearest emergency department if the issue is too urgent to wait. The study staff will instruct the subject to remain at the same dose, increase the dose by 1 capsule or discontinue the study drug in accordance with the protocol. The subject will also be encouraged to contact the study coordinator both before and after the scheduled phone

calls and initial visits if they experience any adverse events or have additional concerns.

The subject will be instructed to discontinue taking all capsules after 8 weeks, regardless of the number of capsules remaining or any improvement experienced on the capsules. No tapering is required prior to stopping treatment.

At the time of enrollment, at the initial study visit, the subject will also be scheduled for an in-office follow-up 8 weeks after starting the capsules (as is standard of care for the treatment of chronic laryngitis). At this visit the subject will be asked to fill out a post-treatment questionnaire including a repeat modified RSI, CSI, VHI-10, and reported overall subjective percentage improvement from baseline. The latter will serve as a separate independent variable, given that neither the RSI, CSI, nor VHI-10 were specifically designed to evaluate chronic laryngeal neuropathy. Any questions the subject might have regarding the questionnaires are answered by the PI.

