The final study visit, after 8 weeks of treatment, will be conducted at no charge to the insurer, and will consist of the post-study paperwork and the discussion of post-study therapy. All visits after the final study visit at 8 weeks after initiating treatment or placebo will be billed to the insurance, unless the visit is to follow up a study related adverse event.

All post-study contact regarding clinical treatment outside of the 10-week study period will be conducted according to standard of care by the clinical office staff and the physician. Given the low dose of amitriptyline prescribed in this study, compared to the usual on-label doses used, no significant adverse effects are anticipated with treatment discontinuation, other than return of symptoms. The usual clinical scheduling staff will handle all scheduling. If the subject needs to come in for study purposes only, the subject will be contacted by phone/email/mail, depending on his/her preference, and asked to come in or provide the information over the phone if possible. They will not be compensated for this additional visit. There will be no financial compensation for subjects.

Personal identifying information collected for the study will not be disclosed to any non-study personnel. Any study personnel found to be using such data in an inappropriate manner will be removed from the study. Subjects' names, medical record numbers, and assigned study subject numbers will be stored on a master Excel spreadsheet and kept on a secured server with access limited to study coordinators and the principal investigator. This will be kept separate from each subject's randomization number and assigned treatment arm, which will be managed by IPS. Only the PI and previously approved clinical investigators will have access to outcomes data. No patient names or medical record numbers will be released or published. The data will be kept for 5 years after the publishing of the results or 10 years after beginning of data collection, whichever comes sooner and then deleted from a secured hospital server. All information will be recorded using subject number, and only the master file will link the study subject number to the subject identifiers.

Safety monitoring/reporting

The study is IND exempt based on prior communications with the Boston Medical Center Institutional Review Board.

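### A request to keep attending after stopping study drug is stated only for adverse-event withdrawals, and the sections on week-8 outcome collection conflict

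*Combined protocol and SAP*

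**What the plan says.** Three places in the combined protocol and SAP bear on whether a subject who stops study drug early contributes a week-8 score.

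- **Study Design** states a retention request tied to one reason for stopping: "If a subject withdraws from treatment due to adverse events, we will ask that they continue coming in for follow-up visits". The same section lets the physician stop study drug for a serious adverse event or a pregnancy. It says nothing about asking subjects to keep attending when they stop for lack of benefit, early relief or personal choice.
- **Study Procedures** makes a universal booking: at enrolment "the subject will also be scheduled for an in-office follow-up 8 weeks after starting the capsules", and the modified RSI, CSI and VHI-10 are repeated there. Weekly calls run through Day 56. Neither is made conditional on still taking capsules, and neither is said to be pursued once a subject has stopped.
- **Analysis (efficacy and safety)** takes it that "subjects who drop out will not have any outcomes recorded", and gives this as the reason that intention-to-treat cannot be done. It then says: "Multiple imputation using the linear regression approach will be used to impute missing data, for subjects who do not complete treatment".

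On the size of the loss, Study Design says "we anticipate the study dropout rate to be approximately 30%, from time of initial enrollment to completion of the post-treatment survey". It reports the pilot "with 5 subjects in each arm dropping out after starting treatment", and adds: "Only three subjects cited adverse events (AEs) as a reason for drop out".

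**The concern.** The primary endpoint is a single questionnaire score at week 8. If the only stated retention request depends on why the subject stopped, whether that score exists may depend on the reason for stopping, and the reason may be linked to how the subject was doing. Subjects are told that they can obtain amitriptyline by prescription outside the study, so one who feels no relief has a reason to leave.

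The planned analysis has little to put against this. The Analysis section says there are no efficacy measurements between baseline and week 8, and the weekly calls are set up to record side effects, concerns and dose, not a symptom score. A regression imputation for an early stopper therefore has no post-baseline efficacy score to draw on.

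The case against intention-to-treat is also partly circular. Scores are expected to be absent, yet for most stoppers the plan does not say that anyone will try to get them. An analysis rule can be revised before unblinding. A week-8 score that was not collected cannot be recovered later.

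**Working it through.** **Inputs**

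- Pilot dropouts after starting drug: 5 + 5 = 10 (Study Design).
- Of these, citing adverse events: 3, two on placebo and one on amitriptyline (Study Design). All three were on study drug, so I count them among the ten.
- Anticipated dropout: 30% (Study Design).
- Planned enrolment: 130, for 100 completers (Analysis).

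**The plan's own figures.** The plan gives no figure for the share of early stoppers outside the retention request. Its enrolment is 100 × 1.30 = 130. That implies either 130 − 100 = 30 dropouts or 0.30 × 130 = 39, so both are carried forward.

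**Step 1: share outside the stated request.** (10 − 3)/10 = 70%. By arm, this is (5 − 1)/5 = 4 of 5 on amitriptyline and (5 − 2)/5 = 3 of 5 on placebo. The exact (Clopper-Pearson) 95% interval for 7 of 10 is:

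- lower limit: 2.5% quantile of Beta(7, 4) = 0.348
- upper limit: 97.5% quantile of Beta(8, 3) = 0.933

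That is 35% to 93%.

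**Step 2: number of subjects, if the pilot split holds (assumption).**

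| Dropouts | Outside request (× 0.70) | Share of 130 |
|---|---|---|
| 30 | 21 | 16% |
| 39 | 27.3, about 27 | 21% |

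**Step 3: uncertainty in the split.** Lower limit with the smaller count: 0.348 × 30 = 10.4, or 8% of 130. Upper limit with the larger count: 0.933 × 39 = 36.4, or 28% of 130.

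**Step 4: the sections side by side.**

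- Study Design expects adverse-event withdrawals to return off drug. Those who do will have a week-8 score, but the Analysis section says that dropouts have none.
- Study Procedures books the week-8 visit for every subject, so a score after stopping is obtainable. The Analysis section treats it as unobtainable.
- The imputation sentence is triggered by not completing treatment, not by a missing score. Read literally, it covers an adverse-event withdrawal who came back and filled in the questionnaire.

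The three sections cannot all be followed as written.

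**The case against.** The strongest reply is that the gap is inferred from silence. The week-8 visit is booked for everyone and the calls through Day 56 carry no on-drug condition. The administration instructions tell patients to consult the investigator before stopping completely, so contact at that moment is intended. The Study Design sentence could be meant as an assurance about adverse-event withdrawals, without excluding anyone else. For visits needed only for the study, Study Procedures lets a subject be "asked to come in or provide the information over the phone if possible", although that paragraph opens on contact after the 10-week period.

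Much of this stands. A reader might infer that only adverse-event stoppers are asked to return and that the rest are never asked for the primary score. The documents do not support that: no post-stopping request is stated for the others, which is a narrower point. The reply does not remove the conflict, because the Analysis section still expects no outcome from dropouts and builds on that expectation.

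The pilot figure is also weak. It rests on ten people, and the other seven reasons are not given. The ten had left the study, and some may have been unreachable or have withdrawn consent, in which case a wider request would not have produced their scores. The 30% is described once as running from enrolment and once as loss during treatment. If it includes people who never started drug, the pilot split does not apply to them.

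Finally, nothing in the documents shows that reasons for stopping differ by arm. Pilot dropout was five in each arm, and more of those citing adverse events were on placebo than on amitriptyline.

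**Conclusion.** The concern holds in this form: a request to keep attending after stopping is stated only for adverse-event withdrawals, and Study Design, Study Procedures and Analysis disagree on whether early stoppers will have a week-8 score. On the pilot split, about 7 in 10 dropouts (exact 95% CI 35% to 93%) fall outside the stated request. That is about 21 to 27 of 130 enrolled (16% to 21%). The size assumes that the pilot split carries over and that pilot dropouts resemble subjects who will stop drug early here.

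Two stronger readings should be resisted. One is that the treatment contrast will be biased by some stated number of points. That needs a score gap between stoppers and completers, and a difference between arms, for which the documents give no figure. Response-related loss is a risk that the planned imputation is poorly placed to correct, not an observed fact. The other is a count built on 100/0.70 = 143 enrolled. That is not the plan's enrolment. It would give 0.30 × 143 = 42.9 dropouts and 0.70 × 42.9 = 30 outside the request, which is still 21%.

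This is more than a missing detail, because the plan followed as written can leave the primary score missing according to the reason for stopping, and the remedy is cheap. It should be changed.

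**What to change.** - **Study Design:** widen the retention sentence from adverse events to any reason for stopping study drug.
- **Study Procedures:** state that the modified RSI, CSI and VHI-10 are sought 8 weeks after starting drug from every randomised subject who has not withdrawn consent to contact, in clinic or by phone or mail. Record the reason and date of stopping, the mode of completion, and any neuromodulator started before week 8.
- **Analysis (efficacy and safety):** replace the statements that dropouts have no outcomes and that intention-to-treat cannot be done. In their place, specify an analysis of all randomised subjects that uses every collected week-8 score and imputes only those still missing. The trigger for imputation becomes a missing score, not incomplete treatment.

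This changes data collection and analysis, not treatment. The visit is already booked and the calls through Day 56 are already scheduled, so the cost is a few sentences and some coordinator time. Phone or mail answers may differ slightly from those given in clinic, which is why the mode is recorded. Some subjects will be unreachable or will decline, so not every score will be recovered.
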